## 10 Withdrawal of Subjects from Study

Subjects may be discontinued from the study for non treatment-related reasons only when no other option is possible. Reasons for discontinuation include, but are not necessarily limited to:

- Voluntary withdrawal from the study by the subject;
- Subject has moved from the area and is determined to be lost-to-follow-up;
- Investigator may discontinue the Subject's participation in the study for reasons including, but not limited to: subject noncompliance, unwillingness or inability to cooperate with study requirements (therapy regimen, follow-up visits, study determination, etc...).

The reason for discontinuation will be recorded on the appropriate case report form.

Prior to discontinuing a subject, every effort should be made to contact the subject in an effort either to get the subject back into compliance with the protocol, or to obtain as much follow-up data as possible. If a subject decides to discontinue from the study, the subject shall have the option of having the system surgically removed followed by normal psychiatric care. Once the patient exits the study, the device will be turned off (no matter what the randomized treatment was assigned). The device can only be reactivated by the study psychiatrist after the patient enters a separate open-label protocol for long-term follow-up. The patient must sign a separate informed consent and must satisfy the inclusion criteria of the long-term follow up study prior to being enrolled. The study psychiatrist must also deem the subject fit to begin or continue with stimulation.

## 11 Data Safety Monitoring Board

A Data Safety Monitoring Board (DSMB) will be appointed to review all SAE data and ensure the appropriate follow up actions necessary. Keeping in mind the safety of patients the status of the study will be evaluated based on a risk to benefit ratio. The Board will create a guidance document prior to the first patient being implanted. This guidance document will indicate the frequency of DSMB meeting, stopping rules and other pertinent information to guide study review.

## **12 Modification of Protocol**

Any amendments to this protocol must be prepared by the study monitor and approved by ANS, the Investigator and the local authority (FDA/IRB/IEC) before implementation.

## **13 Discontinuation of Study**

ANS reserves the right to discontinue any study for administrative reasons at any time, such as but not limited to, a decision to discontinue further clinical investigations with the test article, improper conduct of the study by the Investigator, inability to obtain the number of patients required by the protocol, etc. Reimbursements for reasonable expenses will be made if such action is necessary.

This study may be terminated by the DSMB if an unacceptable number of intracranial hemorrhages or an unacceptable number of completed suicides or suicide attempts is reached without an appropriate explanation. Guidance regarding event evaluation is provided in the DSMB Plan

Study enrollment will be suspended if the following criterion is met until the Data Safety Monitoring Board and FDA can review the safety and effectiveness data to determine whether the study should be halted, modified, or continued.

- If the lower bound of the two-sided 95% confidence interval (based on the normal approximation) for the rate of completed suicides in the combined patient population exceeds 2% at any point during the study.

This study may be terminated if the number of the following events is reached without an appropriate explanation by the 6 month primary endpoint:

- If greater than 24 patients experience an intracranial hemorrhage. This would assume that during the study at the specified interval the rate of intracranial hemorrhage would exceed 12% then the study would be terminated.

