## 3 Study Design

### 3.1 Design

[figure not shown]
This study is designed as a prospective, multi-centered, double-blind, randomized, controlled 12-month pivotal study to evaluate the safety and efficacy of the ANS Libra® Deep Brain Stimulation System for patients with major depressive disorder who have failed at least 4 treatments in the current episode. The primary outcome assessment will occur at 6 months; however, all patients will be followed for 1 year. A total of 201 patients will be randomized from up to 20 sites.

Each potential patient will be pre-screened according to the inclusion/exclusion criteria. A narrative of what study participation entails, will be used to educate potential participants on study requirements. Prior to on-site baseline evaluations, the patient will sign the informed consent. Patients will then undergo 3 baseline evaluations, with each of these evaluations to occur no less than 2 weeks apart from each other. The first 2 baseline visit evaluations will be performed by separate psychiatrists in order to confirm the patient's diagnosis. The patient must score an average  $\geq 22$  on the MADRS, across 3 evaluations. All patients will be scheduled for surgery, to occur no less than two weeks and no more than 1 month after final baseline evaluation, to implant the ANS Libra® Deep Brain Stimulation system. After device implantation, patients will be randomly assigned to 1 of 2 groups in a 2:1 ratio

(Active Treatment Group & Control Group).

[figure not shown]
Group 1: DBS Active Treatment Group – implanted with investigational device and activated for stimulation.

[figure not shown]
Group 2: DBS Control Group – implanted with investigational device, but will not receive active stimulation for the first 6 months of the study. At the end of 6 month visit, these patients will have the investigational device programmed and activated.

[figure not shown]

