## **8 Adverse Events (AEs)**

### **8.1 AE Definitions**

An ADVERSE EVENT is “Any change, undesired, noxious or pathological in a patient or subject illustrated by signs, symptoms and /or laboratory changes that occur during a clinical trial, whether or not considered drug/treatment related.”

A SERIOUS/SEVERE AE is where the event is/causes:

- Life threatening or fatal
- Requires or prolongs hospitalization
- The patient to be disabled

A DEVICE RELATED AE is an anticipated (those events listed in section 8.4) or unanticipated (those events that occur that are not listed in section 8.4) event that occurs that is considered device related. A device-related event is one that the Investigator feels that the device (i.e. IPG, extension or lead) contributed in any way to the adverse event occurring. A stimulation-related event is one that resolves when stimulation is turned off or turned down.

A NON SERIOUS AE is an event other than one described above.

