### **8.3 Reporting AEs**

Throughout the course of the proposed study, all serious/severe adverse events and device related adverse events would be recorded and monitored by the Sponsor and the Investigator. Every effort will be made to remain alert to possible adverse experiences and unexpected findings. If adverse experiences occur, the first concern will be the safety of the subject. Appropriate medical intervention will be made. All completed suicides and suicide attempts (defined by the Columbia Suicide Severity Rating Scale (CSSRS)  $\geq 3$ ) must be reported to the Sponsor immediately (**less than 10 days**) upon discovery. Once the Sponsor is notified of these events, the Sponsor will report these events to the FDA within 10 days.

Individual reports of device related complications will be documented and reported appropriately. The investigator must report all serious AEs to the Sponsor immediately upon discovery by telephone and forward the completed AE form as soon as it is available. The Investigator must also promptly report the resolution to all reported serious or device related AEs.

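### The normal-approximation lower bound makes the suicide suspension rule trigger later than its stated 2% limit and 95% level imply; an exact bound would correct this

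*Combined protocol and SAP*

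**What the plan says.** Section 13 (Discontinuation of Study) contains one suicide criterion that carries a number and obliges action. Enrolment is suspended, pending review by the Data Safety Monitoring Board (DSMB) and FDA, on a condition that begins: "If the lower bound of the two-sided 95% confidence interval (based on the normal approximation) for the rate of completed suicides". The section gives no formula and no table of counts. On population, limit and timing the criterion reads: "in the combined patient population exceeds 2% at any point during the study". It pools the two groups but does not say whether enrolled, implanted or randomized patients form the denominator.

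The same section also lets the DSMB terminate the study if "an unacceptable number of completed suicides or suicide attempts is reached without an appropriate explanation", which is discretionary and carries no number. It refers to a DSMB Plan for guidance on evaluating events, and Section 11 says that a DSMB guidance document will contain stopping rules. Neither is among the documents.

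Other safeguards exist. Section 8.3 has completed suicides and attempts reported to the sponsor and adds: "Once the Sponsor is notified of these events, the Sponsor will report these events to the FDA within 10 days". Section 8.1 includes "Life threatening or fatal" in its definition of a serious event, and under Section 11 the DSMB "will be appointed to review all SAE data".

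**The concern.** The rule may be applied at any time, so it will usually be applied to a handful of events. The Wald interval is weakest there. It computes the standard error at the observed rate, so a run of events that raises the estimate also widens the interval and pulls the lower bound back down. A reader who sees a 95% interval and a 2% limit would expect the bound to cross wrongly about 2.5% of the time at a single look. If the real figure is far smaller, the rule is less sensitive than it appears.

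What is at stake is the timing of the automatic pause. Section 3.1 says: "After device implantation, patients will be randomly assigned to 1 of 2 groups in a 2:1 ratio". Patients in both groups therefore undergo surgery before assignment, and until the pause further patients in both groups can be implanted.

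**Working it through.** **Inputs.** Limit 2%, two-sided 95% (z = 1.96, lower tail 2.5%) and normal approximation, all from Section 13. Maximum n = 201, from Section 3.1. The documents state no trigger count, so there is none to reproduce.

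**Formulas.** For x suicides among n patients, with p = x/n:
- Wald lower bound: p − 1.96 × √(p(1−p)/n).
- Exact (Clopper-Pearson) lower bound: the 2.5% quantile of a Beta(x, n−x+1) distribution.
- Trigger count: the smallest x whose lower bound exceeds 0.02.
- Single-look rate: P(X ≥ trigger count) for X binomial(n, 0.02).

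**Worked case, n = 100.**
- Wald, 7 suicides: 0.07 − 1.96 × √(0.07 × 0.93/100) = 0.07 − 1.96 × 0.02551 = 0.01999. This does not exceed 2%.
- Wald, 8 suicides: 0.08 − 1.96 × 0.02713 = 0.02683. Trigger count 8.
- Exact: 5 suicides give 0.01643 and 6 give 0.02233. Trigger count 6.

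The reason shows in the standard error. At 7/100 Wald uses 0.0255, whereas at a true 2% the standard error is √(0.02 × 0.98/100) = 0.0140.

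**Other sizes.**

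| n | Wald count | Exact count | Wald single-look rate at true 2% | Exact single-look rate at true 2% |
|---|---|---|---|---|
| 30 | 5 | 3 | 0.03% | 2.2% |
| 50 | 6 | 4 | 0.05% | 1.8% |
| 99 | 7 | 6 | 0.38% | 1.5% |
| 100 | 8 | 6 | 0.09% | 1.5% |
| 125 | 8 | 7 | 0.38% | 1.3% |
| 201 | 11 | 9 | 0.26% | 2.1% |

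**All sizes.** At n = 1 to 3 the two methods need the same count. From n = 4 to 201 (198 sizes) Wald needs one more at 126 and two more at 72, and never the same number. The highest single-look rate over that range is 0.70% for Wald (n = 198) and 2.47% for exact (n = 142). Exact is also conservative, but it comes close to the nominal 2.5% without passing it.

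**Repeated looks.** Neither bound adjusts for looking at any point. The chance of at least one false suspension at a true 2%, up to patient 201, is:

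| Setting (assumptions, not protocol figures) | Wald | Exact |
|---|---|---|
| Outcome known at entry, looks from n = 10 | 1.4% | 8.4% |
| Outcome known at entry, looks from the first patient | 3.4% | 9.8% |
| Suicides spread evenly over 12 months, 3 patients entering a month | about 0.6% | about 3.3% |
| Same, 5 a month | about 0.4% | about 1.8% |
| Same, 10 a month | about 0.1% | about 0.5% |

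The first two rows are exact binomial recursions. The last three are simulations (40,000 trials each) that check the rule at each suicide while enrolment is open, from n = 10, with patients implanted to date as the denominator.

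**The case against.** The strongest objection concerns the yardstick. The rule is monitored continuously, so a single-look 2.5% is not its operating characteristic. With outcomes known at entry, Wald's cumulative 1.4% or 3.4% is nearer 2.5% than the exact bound's 8.4% or 9.8%. With delayed events the comparison is mixed. The documents state no target false-suspension rate, so preferring the exact bound could be called a preference about conservatism. Part of this stands: the price of the change must be shown, and the sponsor may decide that it prefers the Wald counts. But the protocol defines its rule by a limit and a confidence level, and Wald does not deliver that level. If protection against repeated looks was intended, it should be designed and stated, not left to arise from a poor approximation.

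Three stronger readings are tempting and are not supported.

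- *The rule is undefined.* A Wilson score interval also rests on a normal approximation and would need 5 suicides at n = 100 against Wald's 8. But Wald is the ordinary reading, and n = 100 is the first size at which Wald needs 8 (at n = 99 it needs 7). The three-event gap occurs at only 45 of the 198 sizes. The DSMB Plan may fix the formula and denominator. This is a point to clarify, no more.
- *Suicides could go unreviewed until the rule triggers.* They could not: each goes to FDA and, as a fatal serious event, to the DSMB, which may act on its own.
- *The rule fails because it stays silent at observed rates above 2%.* The limit applies to the lower bound, so any interval method does this. At n = 100 the exact bound is silent at 5.

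The hemorrhage rule in the same section does print a count ("If greater than 24 patients experience an intracranial hemorrhage"), but it is tied to the 6-month endpoint. A rule applied at every n needs a table, so that contrast carries little weight.

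**Conclusion.** The concern holds for the interval method. On the ordinary reading, the suspension rule needs one or two more suicides than an exact bound at the same limit and level, at every size from 4 to 201; one is the commoner gap. Its single-look rate at a true 2% is at most 0.70% against a nominal 2.5%. The error runs in the direction that delays a mandatory pause. This rests only on the protocol's 2%, 95% and 201 and on reading the normal approximation as Wald. The cumulative false-suspension figures rest in addition on the assumed entry rates and event timing.

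The finding does not say that 2% is the right or wrong limit, and the consequence of crossing it is a pause for review, not termination. The unnamed formula and denominator are secondary, and can be called open only in the documents seen here. The point should be fixed, and the change is small.

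**What to change.** In Section 13, keep the 2% limit and the 95% level, and replace the parenthesis naming the normal approximation with one naming the exact (Clopper-Pearson) interval. State the denominator, for example all patients implanted to date. Add a short table of trigger counts by n; under the exact bound these are 3 at 30, 4 at 50, 6 at 100, 7 at 125 and 9 at 201. Beside it, give the false-suspension rate under repeated looks with its assumptions. Make the DSMB Plan agree.

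The drafting cost is a few words and one table. The operating cost is the rise in false pauses shown in the repeated-looks table, which the sponsor should accept knowingly. If the sponsor prefers the Wald counts for that reason, it should name the formula, print its counts and give the reason, so that the rule can be applied from its own text.

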## Protocol Summary

Title:	A clinical evaluation for the management of patients with Major Depressive Disorder, single or recurrent episode, with deep brain stimulation.
Test Articles:	ANS Libra® Deep Brain Stimulation System
Objectives:	To demonstrate the safety and efficacy of deep brain stimulation (DBS) to the subgenual white matter (Brodmann Area 25WM) as an adjunctive treatment for single or recurrent Major Depressive Disorder (MDD).
Patient Population:	Patients who have single or recurrent Major Depressive Disorder (MDD) complying with specific inclusion/exclusion criteria.
Sample Size:	A total of 201 patients will be randomized to treatment from up to 20 investigational sites.
Structure:	Prospective, controlled, multi-centered, double blind, randomized, study with endpoint evaluation at 6 months post device implantation. Control group patients will not have the investigational device activated for the first 6 months of study.
Method of Assignment:	All patients who meet the inclusion/exclusion criteria will be randomized.
Randomization:	Randomization will be performed according to a computer generated scheme after device implant in a 2:1 ratio (Active Stimulation vs. Control Group).
Statistical Analysis:	The primary endpoint, at least a 40% decrease from baseline to 6 months in Montgomery and Asberg Depression Rating Scale (MADRS) and no worsening in Global Assessment of Functioning, will be analyzed by logistic regression that includes the effects of treatment group, study site, and baseline MADRS, and will be tested at the 5% level of significance.
Adverse Events:	Volunteered and solicited.

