### **9.7.2 Other Analyses of Safety**

### **9.8 Stopping Rule for Futility**

The futility analysis will be done when 75 to 100 patients have achieved the primary endpoint by either completing their Month-6 visit or have terminated from the trial prior to their Month 4 visit. No more than 125 patients will be enrolled into the trial until the results of the futility analysis have been completed and reviewed by FDA.

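### The 2% suicide suspension limit has no time horizon or defined denominator; if all entered patients are counted, staggered entry raises the trigger by about 0 to 3 events while enrolment is open

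*Combined protocol and SAP*

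**What the plan says.** Section 13 (Discontinuation of Study) contains one quantified, mandatory trigger for suicide: "Study enrollment will be suspended if the following criterion is met until the Data Safety Monitoring Board and FDA can review" the data. The criterion is that the lower limit of a two-sided 95% normal-approximation interval "for the rate of completed suicides in the combined patient population exceeds 2% at any point during the study". The section does not say whether the denominator is patients enrolled, implanted or randomised, patients with some minimum follow-up, or patient-time. It does not say over what period the 2% applies.

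Three other statements matter here:

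- Section 3.1: "A total of 201 patients will be randomized from up to 20 sites", and "The primary outcome assessment will occur at 6 months; however, all patients will be followed for 1 year".
- Section 9.8: "No more than 125 patients will be enrolled into the trial until the results of the futility analysis have been completed and reviewed by FDA". The futility analysis itself takes place when 75 to 100 patients have reached the endpoint.
- Section 13, next rule: possible termination above 24 intracranial haemorrhages, linked to a rate of 12% and to the 6-month endpoint. That rule names an interval of follow-up; the suicide rule does not.

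**The concern.** Patients enter over time, and each is followed for a year. A fixed percentage checked at every point therefore refers to a different amount of follow-up at each look. If everyone entered so far is in the denominator, a patient implanted last week counts the same as one followed for twelve months.

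The rule's only action is to suspend enrolment, so it can protect new patients only while enrolment is open. That is also when a crude proportion understates the one-year risk most. The rule would be least sensitive at the time when it can do most good.

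**Working it through.** **Is there a figure to reproduce?** The suicide rule states no event count and no operating characteristics. The neighbouring haemorrhage rule is consistent with the planned total: 0.12 × 201 = 24.1, and 24/201 = 11.9%. This supports reading a percentage in this section as events divided by patients.

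**Inputs from the plan.** 201 patients, 12 months of follow-up each, both arms pooled, z = 1.96, limit 2%, hold at 125 enrolled.

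**Assumptions, because the plan gives no accrual or suicide rate.** Uniform entry over 12 to 48 months, constant hazard, and 2% read as 2 per 100 patient-years.

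**Step 1: trigger when all entered patients are counted.** Find the smallest x with x/n − 1.96·√[(x/n)(1 − x/n)/n] > 0.02.

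- n = 100: 7 suicides give 1.999%, just short, so 8 are needed.
- n = 125: 7 give 1.57% and 8 give 2.11%, so 8.
- n = 201: 10 give 1.97% and 11 give 2.33%, so 11.

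**Step 2: trigger per patient-year.** Find the smallest x with (x − 1.96·√x)/PY > 0.02, that is PY < (x − 1.96·√x)/0.02. A count of 5 triggers below 30.9 patient-years, 6 below 59.95, 7 below 90.7, 8 below 122.8, 9 below 156.0, 10 below 190.1 and 11 below 225.0.

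**Step 3: patient-years observed when the nth patient enters.** With r entries per year, PY = n²/(2r) if n ≤ r, otherwise n − r/2. For 24 months, r = 100.5. At n = 100, PY = 10,000/201 = 49.8; at n = 201, PY = 201 − 50.25 = 150.8.

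| Accrual | n = 100: PY, trigger | n = 125: PY, trigger | n = 201: PY, trigger |
|---|---|---|---|
| All entered counted | 8 | 8 | 11 |
| 12 months | 24.9, 5 | 38.9, 6 | 100.5, 8 |
| 18 months | 37.3, 6 | 58.3, 6 | 134.0, 9 |
| 24 months | 49.8, 6 | 74.8, 7 | 150.8, 9 |
| 36 months | 66.5, 7 | 91.5, 8 | 167.5, 10 |
| 48 months | 74.9, 7 | 99.9, 8 | 175.9, 10 |

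The difference is 0 to 3 events. The table ignores the hold at 125; when the hold lifts, the comparison is 8 against 7 or 8.

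**Step 4: chance of suspension before enrolment closes.** This was simulated at a true 6 per 100 patient-years, with the rule checked at each event. The hold at 125 was included, with futility at 100 patients and an assumed 2-month review.

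| Accrual apart from the hold | All entered | Per patient-year |
|---|---|---|
| 18 months | about 40% | about 55% |
| 24 months | about 44% | about 58% |
| 36 months | about 53% | about 63% |

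Without the hold, the 24-month contrast would look larger, at about 37% against 57%.

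**Step 5: how much is due to the interval.** Two per cent of 100 patients is 2 suicides, and of 201 about 4. With complete one-year follow-up the criterion still needs 8 and 11 on either denominator. Changing only the interval, with all entered patients counted, gives 6 (Wilson) or 7 (exact) instead of 8 at n = 125, and 8 or 9 instead of 11 at n = 201. Dilution remains with exact limits: 6 against 4 at n = 100 under 24-month accrual.

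**The case against.** The strongest reply is that section 13 never says suicides are divided by all patients. The word for the pooled population most naturally means both arms together, and the DSMB Plan, which is not among these documents, may define the denominator. This stands: the dilution is a consequence of a plausible reading, and what the text itself shows is that denominator and horizon are undefined. But a suspension trigger should not depend on who picks the denominator.

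A reader might also infer that the pause comes too late, or that nothing else guards against an excess of suicides. The documents do not support either.

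- **Timing.** The size rests on accrual and suicide rates that the plan does not give. At the 125-patient point the difference is 0 to 2 events, and the hold narrows it further. Constant hazard is also assumed; if risk were concentrated soon after implantation, dilution would be smaller.
- **Other safeguards.** Section 13 lets the DSMB terminate for too many suicides or attempts without any interval condition. Section 11 has the DSMB review all serious events and set its own stopping rules before the first implant. Section 8.3 requires suicides to reach the sponsor in under 10 days and FDA within a further 10. These are real, but the DSMB termination route is discretionary and has no number in these documents.

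Finally, writing the limit per patient-year chooses a horizon. If 2% was meant as a 6-month risk, 2 per 100 patient-years would roughly halve it. That stands, and only the sponsor can settle it.

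**Conclusion.** The point holds in a limited form. The 2% limit has no exposure time or horizon. On the natural reading, the plan's only quantified mandatory suicide trigger fires later during accrual than a rule based on follow-up time, by about 0 to 3 events. At a true 6 per 100 patient-years, this lowers the chance of suspending before enrolment closes by about 10 to 15 percentage points over 18- to 36-month accrual, given uniform entry, constant hazard, the hold at 125 and a 2-month review.

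Dilution is not the main reason that the bar is high. Requiring a normal-approximation lower limit above 2% is a separate and larger cause. The change is worthwhile and cheap, but its absence does not leave the trial without suicide monitoring.

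**What to change.** In section 13 and the DSMB Plan:

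1. Base the rule on completed suicides per patient-year from implantation, both arms pooled, ending at the earliest of death, exit, 12 months or the data cut. The alternative is the Kaplan-Meier 12-month risk, which cannot be estimated until some patients have been followed that long.
2. Have the sponsor confirm that 2% refers to 12 months.
3. Keep the interval type named in the text.
4. Report operating characteristics: the trigger count by patient-years, and the chance of suspension over a range of true rates and accrual speeds, with the hold at 125 included.

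**Cost.** A short change of wording in two documents; the dates needed are those of implantation, death and exit. At a true 2 per 100 patient-years the chance of a precautionary pause rises slightly with the normal approximation: about 0.3% to 1% at any time without the hold, or about 0.4% to 0.8% before enrolment closes with it. It would be about 9 to 10% with exact Poisson limits, because one suicide would trigger before 1.27 patient-years and two before 12.1. This is why the interval must be named.

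The end-of-study trigger stays at 11 for 201 full patient-years. It becomes 10 if early exits, which sections 7.4 and 10 allow, reduce follow-up to about 190, since (10 − 1.96·√10)/0.02 = 190.1.
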